The Emory University IRB, the OHRP, FDA, or other government regulatory authorities may perform clinical site monitoring. Clinical research sites monitoring may include the review of the individual participant records, including consent forms, CRFs, supporting data, laboratory specimen records, and medical records (physicians' progress notes, nurses' notes, individuals' hospital charts) to ensure protection of study participants, compliance with the protocol, and accuracy and completeness of records. The monitors may also inspect sites' regulatory files to ensure that regulatory requirements are being followed.

The investigators will make study documents (e.g., consent forms, CRFs) and pertinent hospital or clinic records readily available for inspection by the local IRB or the OHRP for confirmation of the study data.

ADVERSE EVENT MONITORING AND REPORTING

Adverse events (AEs) will be reported on an expedited basis at the standard level during the protocol-defined expedited adverse event (EAE) Reporting Period, which is the entire study

duration for an individual subject (from study enrollment until study completion or discontinuation of the subject from study participation for any reason).

AE Reporting

Any AE that is reported to either the investigators or their designated research associates by a study subject or by medical staff caring for the subject and which meets the criteria will be documented.

In addition, clinical investigators will monitor subjects for AEs during each study visit. Any AE will be reported to the Emory University IRB within 10 days of the event, and any serious adverse event (SAE) will be reported to the IRB within 24-48 hours of the event. The standard Emory IRB reporting guidelines for AE and SAE reporting, as documented at http://www.emory.edu/IRB/guidelines_adverse_event.php, will be followed.

A SAE is an adverse drug experience that results in any of the following outcomes:

1. Death.
2. Life-threatening situation - The subject was at risk of death at the time of the adverse event/experience. It does not refer to the hypothetical risk of death if the AE were more severe or were to progress.
3. Inpatient hospitalization or prolongation of existing hospitalization.
4. Persistent or significant disability/incapacity - Any AE having an outcome that is associated with a substantial disruption of the ability to carry out normal life functions, including the ability to work. This is not intended to include transient interruption of daily activities.
5. Congenital anomaly/birth defects - Any structural abnormality in subject's offspring that occurs after intrauterine exposure to treatment.
6. Important medical events/experiences that may not result in death, be life-threatening, or require hospitalization may be considered a serious adverse event/experience when, based upon appropriate medical judgment, they may jeopardize the subject and may require medical or surgical intervention to prevent one of the outcomes listed above, i.e., death, a life-threatening adverse event/experience, inpatient hospitalization or prolongation of existing hospitalization, a persistent or significant disability/incapacity, or a congenital anomaly/birth defect. Examples of such medical events/experiences include allergic bronchospasm requiring intensive treatment in an emergency room or at home, blood dyscrasias or convulsions that do not result in inpatient hospitalization, or the development of drug dependency or drug abuse.
7. Spontaneous and elective abortions will be reported to the Emory IRB as serious adverse events.

8. Severity of AEs will be rated according to the following definitions:

Mild: The adverse event is transient and easily tolerated by the subject.

Moderate: The adverse event causes the subject discomfort and interrupts the subject's normal activities.

Severe: The adverse event causes considerable interference with the subject's normal activities and may be incapacitating or life-threatening.

The following definitions will be used to assess the relationship of the AE to study drugs or procedures:

Probably Related: An adverse event has a strong temporal relationship to study drug or recurs on re-challenge, and another etiology is unlikely or significantly less likely.

Possibly Related: An adverse event has a strong temporal relationship to the study drug, and an alternative etiology is equally or less likely compared to the potential relationship to study drug.

Probably Not Related: An adverse event has little or no temporal relationship to the study drug and/or a more likely alternative etiology exists.

Not Related: An adverse event is due to an underlying or concurrent illness or effect of another drug and is not related to the study drug (e.g., has no temporal relationship to study drug or has much more likely alternative etiology).

If the adverse event is in, the investigator's opinion, possibly or probably related, or not related to study drug or procedures, then an alternate etiology will be provided by the investigator.

It should however be noted that a severe adverse event /experience is not necessarily serious, as the term severe is a measure of intensity while a serious adverse event (SAE) is determined based on the aforementioned regulatory criteria.

TITLE OF PROJECT: PrEP, LUBE, AND THE RECTAL MUCOSA IN MSM AT RISK OF HIV

Emory IRB00077593

PRINCIPAL INVESTIGATOR: [name], MPH

All AEs and laboratory abnormalities will be graded according to the Division of AIDS Table for Grading the Severity of Adult and Pediatric Adverse Events (DAIDS AE Grading Table), Version 1.0, December 2004, which can be found on the DAIDS RCC Web site: http://rcc.tech-res.com/tox_tables.htm. All AEs will be followed to satisfactory clinical resolution.

DATA SAFETY MONITORING

Summaries of adverse events (Grades 3 or 4), and targeted AEs across study groups as well as study conduct will be reviewed regularly (in real time and summarized quarterly) by study investigators. Any AE will be reported to the Emory University IRB within 10 days of the event, and any SAE will be reported to the IRB within 24-48 hours of the event. The standard Emory IRB reporting guidelines for AE and SAE reporting, as documented at http://www.emory.edu/IRB/guidelines_adverse_event.php, will be followed.

Additional safety monitoring will be performed annually by an independent Medical Safety Monitor. Based on the 1 year accrual expectation for the study, it is anticipated that the study will undergo 2 reviews by the Medical Safety Monitor. The first will occur approximately 6 months after the accrual of the first subject. The safety report will summarize AEs and SAEs by study group. The DCC will work with the Medical Safety Monitor to complete a 'final assessment' following the review of each safety report. As part of the final assessment the Medical Safety Monitor will conclude 'the study can continue as no safety concerns have been identified at the time of the review' or 'the study cannot continue as currently designed'. The final assessment by the Medical Safety Monitor will be provided to the study PI who will make the findings available as appropriate to the Emory IRB and the NIH.

STUDY DISCONTINUATION

A study participant may elect to discontinue participation in the study at any time. The study may be discontinued at any time by the IRB, the OHRP, or other government agencies as part of their duties to ensure that research subjects are protected.

BIOHAZARD CONTAINMENT

As the of blood-borne pathogens can occur through contact with contaminated needles, blood, and blood products, appropriate blood and secretion precautions will be employed by all personnel in the drawing of blood and handling of all specimens for this study, as currently recommended by the Centers for Disease Control and Prevention and the National Institutes of Health.

All infectious specimens will be transported using packaging mandated in the Code of Federal Regulations, 42 CFR Part 72.

BIOSAFETY PLAN

TITLE OF PROJECT: PrEP, LUBE, AND THE RECTAL MUCOSA IN MSM AT RISK OF HIV
Emory IRB00077593
PRINCIPAL INVESTIGATOR: [name], MPH

No specific biosafety plan is necessary for this protocol as all planned immunologic and genetic assays will fall under the existing biosafety protocols of the Hope Clinic and CDC.

REFERENCES

1. Service UPH. Pre-exposure Prophylaxis for the Prevention of HIV Infection in the United States-2014: A Clinical Practice Guideline. 2014.

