Design: To address the impact of a popular, over-the-counter gel lubricant use in MSM on PrEP, investigators at Emory University will collaborate with the Centers for Disease Control and Prevention (CDC) to conduct a randomized clinical trial of 90 MSM. Men will be randomized into a 3-arm study as follows: (1) daily oral Truvada® only, (2) daily gel lubricant applied rectally only or (3) oral Truvada® plus rectal gel lubricant application daily. This study will entail 4 study visits at the Emory University Hope Clinic. During the first visit (time 0), all men will be screened for eligibility and undergo written informed consent, physical examination, rapid HIV testing, phlebotomy for screening laboratories, and randomization. During study visit 2 prior to the initiation of study product (time 1-6 weeks), participants will undergo phlebotomy, collection of rectal secretions, and rectal biopsy via rigid sigmoidoscopy for establishment of baseline values. During study visit 3 (time 4-16 weeks), men will be dispensed and instructed on the at-home application of rectal lubricant and/or oral Truvada. During study visit 4 (time 5-26 weeks), men will return after 7 consecutive days of study product use for repeat phlebotomy, collection of rectal secretions, and rectal biopsy via rigid sigmoidoscopy. After collection, biologic specimens will be immediately transported by courier to CDC (laboratory of [name]) for processing. Specimens will be processed immediately for *ex vivo* laboratory assays that will include PrEP drug concentrations, inflammatory cytokine levels, HIV target cell measurement and characterization by flow cytometry, and *in vitro* HIV infection assays. Comparison of assay results among the 3 study arms should determine if rectal lubricant usage reduces PrEP drug concentrations, increases inflammation, or increases the proportion or susceptibility of HIV target cells in the rectal mucosa.

Duration: The duration of this study is 2 years. Participants will be considered 'on-study' for no more than 26 weeks.

Sample size: For this protocol we will recruit 90 HIV-negative MSM who meet eligibility criteria outlined in the protocol.

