To address the impact of a popular, over the counter, gel lubricant use in the rectum in MSM on PrEP, investigators at Emory University will collaborate with [name] at the CDC to recruit and randomize 90 MSM into a three-arm study of PrEP and lubricants: (1) daily oral Truvada® for 7 days, (2) daily gel lubricant applied rectally for 7 days or (3) oral Truvada® plus rectal gel lubricant application daily for 7 days. At CDC, *ex vivo* laboratory assays will be used to evaluate the impact of rectal lubricant use on oral PrEP's effectiveness. Blood, rectal secretions and rectal biopsies obtained by rigid sigmoidoscopy (at approximately 8 -10 cm from the anal verge) will be collected from men in all three study arms at least 21 days prior to initiation of treatment and immediately following 7 days of consecutive use of assigned product. Specimens will be processed immediately for *ex vivo* laboratory assays at CDC. Blood plasma and PBMCs will be used to measure extracellular and intracellular drug concentrations as well as intracellular concentrations of the natural dNTP substrates to assess adherence to oral Truvada® and to compare changes in the ratio of drug to natural substrate in peripheral blood. Rectal secretions from all participants will be analyzed to measure changes in soluble immunological cytokines in the presence of gel lubricant usage that may indicate associated increases in inflammation. Rectal lymphocytes will be isolated from the rectal biopsies collected from each man and analyzed for concentrations of intracellular tenofovir and emtricitabine as well as natural substrates, dATP and dCTP, to evaluate the potential for gel lubricant to alter the ratio of antiretroviral drug to natural substrate in the rectal mucosa. Additionally, rectal lymphocytes from 10 participants in each arm will be characterized using multicolor flow cytometry to observe potential changes in the proportion and activation state of HIV target cells within the rectal mucosa. Rectal lymphocytes from the remaining 10 participants in each arm will be subjected to *in vitro* infection with HIV to test for changes in the susceptibility to virus infection in the presence of gel lubricant usage.

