These studies should provide important laboratory results to help inform policy and public health officials as to usage of hyperosmolar rectal lubricants in concert with oral PrEP. Pharmacological analyses will provide important data as to whether lubricant usage diminishes the ratio of drug to substrate in HIV target cells in the rectum that may reduce PrEP effectiveness. Immunological studies will help us understand whether lubricant usage

9/26/16

TITLE OF PROJECT: PrEP, LUBE, AND THE RECTAL MUCOSA IN MSM AT RISK OF HIV

Emory IRB00077593

PRINCIPAL INVESTIGATOR: [name], MPH

increases inflammation and the concentrations of HIV target cells in the rectum of men taking oral PrEP. The *ex vivo* virus infection assays described here will provide a surrogate measure of whether lubricant usage increases susceptibility to rectal infection with HIV for men taking oral PrEP. Together the combination of these studies should help determine if rectal lubricant usage may abrogate the potential anti-HIV benefits of oral PrEP.

Public Health Relevance: Information about the impact of rectal lubricant use in men who have sex with men will better inform policy makers and the public to make important choices regarding the safety of rectal lubricant usage in the presence of pre-exposure prophylaxis.

Goal: To determine if PrEP efficacy can be abrogated by use of rectal lubricants in MSM.

STUDY POPULATION

A total of 70 HIV-negative MSM aged 18-49 will be recruited from existing Emory University study databases of MSM who have agreed to future contact about research opportunities. We will also recruit men from print and on-line advertisements. Research recruiters at the Hope Clinic and the Rollins School of Public Health are experienced in recruiting this population for research studies, including those with rectal biopsies, and do not anticipate problems. [name] is currently conducting an Emory IRB approved study of the effects of unprotected anal intercourse on the rectal mucosa. This study involves recruiting a similar population to undergo repeated rectal biopsy procedures that are timed with sexual intercourse. We expect approximately 10-15% of men will not complete the study, therefore the sample size of 70 men will likely result in study completion for 60 men.

INCLUSION CRITERIA FOR MSM

- 1) HIV-negative man who reports receptive anal sex with another man in the last 6 months aged 18-49 years

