TITLE OF PROJECT: PrEP, LUBE, AND THE RECTAL MUCOSA IN MSM AT RISK OF HIV

Emory IRB00077593

NCT02401230

PRINCIPAL INVESTIGATOR: [name], MPH

19Jan2018

STATISTICAL ANALYSIS PLAN

Drug and dNTP concentrations were normalized to fmol/million cells and fmol/mg rectal tissue in blood and tissue, respectively. Detectable drug and dNTP concentrations as well as immune cell proportions were compared between the Truvada, Rectal Gel Lubricant and Rectal Gel Lubricant + Truvada study arms using a Wilcoxon Rank Sum Test. Left censoring was observed for drug concentration measurements below the limit of detection.

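### For immune cell and infection readouts, the three-arm comparison shows the lubricant effect in men taking Truvada, not that lubricant abrogates PrEP

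*Protocol*

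**What the plan says.** The Goal in the Protocol's Project Description is "To determine if PrEP efficacy can be abrogated by use of rectal lubricants in MSM". The Design section lists the arms as "1) daily oral Truvada® only, (2) daily gel lubricant applied rectally only or (3) oral Truvada® plus rectal gel lubricant application daily". No arm goes without product.

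The same section expects that "Comparison of assay results among the 3 study arms should determine if rectal lubricant usage reduces PrEP drug concentrations, increases inflammation", and goes on to the proportion and susceptibility of HIV target cells. The Project Description assigns rectal lymphocytes from 10 men per arm to flow cytometry and from the remaining 10 per arm to an in vitro infection assay, the latter "to test for changes in the susceptibility to virus infection in the presence of gel lubricant usage".

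The SAP is one paragraph. "Detectable drug and dNTP concentrations as well as immune cell proportions were compared", and these measurements "were compared between the Truvada, Rectal Gel Lubricant and Rectal Gel Lubricant + Truvada study arms using a Wilcoxon Rank Sum Test". It mentions no baseline value, change score or interaction, and it does not list the infection assay.

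Product-free samples do exist. Blood, secretions and biopsies "will be collected from men in all three study arms at least 21 days prior to initiation of treatment", and the Design section describes the visit 2 "rectal biopsy via rigid sigmoidoscopy for establishment of baseline values".

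**The concern.** To say that lubricant abrogates PrEP is to say that PrEP does less when lubricant is used. That sets one PrEP effect (combination against lubricant alone) beside another (Truvada against no product). The trial has three of those four cells as randomised arms.

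If lubricant raises target cells or susceptibility in everyone, on PrEP or not, combination will exceed Truvada and the result could be written up as lost PrEP benefit. The Protocol means to inform policy makers. A message that lubricant raises susceptibility in all users differs from a message that lubricant defeats PrEP, and the planned comparisons cannot tell the two apart.

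**Working it through.** The documents give no alpha, power, effect size or SD, so there is no planned figure to reproduce. The inputs are the three arms (Protocol, Design), the 10 men per arm for each laboratory subset (Project Description) and the between-arm test (SAP). I read the SAP's comparison as one of post-product values, since it mentions no baseline. Assumed: a normal outcome on a suitable scale, a visit 2 to visit 4 correlation ρ of 0.5, and two-sided 0.05.

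**1. What the three arms estimate.** Write a cell mean as m0 + P (PrEP) + L (lubricant) + PL (change in PrEP's effect when lubricant is added).
- Combination − Truvada = L + PL
- Combination − lubricant = P + PL
- Truvada − lubricant = P − L

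The third is the second minus the first, so there are two independent equations for three unknowns. PL cannot be recovered, however many men are enrolled.

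**2. Two opposite truths, same arm means** (illustrative susceptibility scale).

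| | m0 | P | L | PL | Truvada | Lubricant | Combination |
|---|---|---|---|---|---|---|---|
| 1.0 of a 1.5 PrEP benefit lost | 2.5 | −1.5 | 0 | +1 | 1.0 | 2.5 | 2.0 |
| No benefit lost, lubricant adds 1.0 for everyone | 1.5 | −0.5 | +1 | 0 | 1.0 | 2.5 | 2.0 |

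Only the product-free mean (2.5 or 1.5) separates them.

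**3. Drug measurements.** Without Truvada there is no drug, so m0 = L = 0 and combination − Truvada = PL. For drug concentration and the drug-to-substrate ratio, that comparison measures the loss directly.

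**4. How often combination versus Truvada is significant when PL = 0** (simulated rank-sum test).

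| Men per arm | L = 0.5 SD | L = 1 SD |
|---|---|---|
| 10 | 16% | 51% |
| 20 | 32% | 85% |

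The row for 10 matches the flow cytometry and infection subsets; 20 is shown for range. These are correct detections of a lubricant effect in men on Truvada. They become errors only if reported as lost PrEP effect.

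**5. What the visit 2 sample adds.** Let D be the change from visit 2 to visit 4, and T any shift between those visits that occurs without product.
- D(both) − D(lubricant) − D(Truvada) estimates (P + L + PL + T) − (L + T) − (P + T) = PL − T.
- Its SE is SD × √(3 × 2(1 − ρ)/n) = √(3/10) = 0.55 SD at n = 10. Combination versus Truvada at visit 4 has SE √(2/10) = 0.45 SD.
- For 80% power it needs PL of about (1.96 + 0.84) × 0.55 = 1.5 SD.
- With PL = 0, its false-positive rate (noncentral t) is 5% at T = 0, about 14% at T = 0.5 SD and 42% at T = 1 SD, with 10 per arm.

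A non-zero T is plausible. The inclusion criteria ask for 3 days without receptive anal intercourse before visit 2 but 10 days before visit 4, and visit 4 follows an earlier biopsy session. If inflammation falls with longer abstinence, T is negative and the bias is towards apparent abrogation.

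**The case against.** The strongest reply is that the Protocol does not define abrogation as an interaction. Its Project Description says protection may be lost through epithelial damage, inflammation and immune activation, and it frames the laboratory questions around men who are taking oral PrEP. Combination versus Truvada answers those questions, is randomised, and is free of T. This stands: the planned comparison is sound for the narrower question, and only the wider conclusion lacks support.

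Interaction also depends on scale. Suppose infection is 100 with no product, 200 with lubricant, 20 with Truvada and 40 with both. PrEP cuts infection by 80% with or without lubricant, yet by 80 units without it and 160 with it. This stands too, so the scale must be fixed before the data are seen.

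Three stronger readings are tempting, and the documents do not support them.
- A reader might infer that the drug analyses share the defect. Step 3 shows that they do not.
- A reader might infer that the SAP's rank-sum test is assigned to the infection assay. The SAP does not list that assay; only the Design section's general three-arm comparison covers it.
- A reader might infer that the baseline-change interaction should be required before any conclusion. It would replace a randomised comparison with a less precise one that T can bias, and the Protocol's own visit conditions make T likely enough to matter.

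**Conclusion.** The concern holds in a limited form. For immune cell proportions, and for in vitro infection under the Design section's general comparison, the planned between-arm tests estimate the lubricant effect in men taking Truvada. They do not by themselves support a conclusion that PrEP's effect is abrogated. The gap is one of identification, so it does not depend on the assumed values. The percentages do: they rest on assumed effect sizes, normal outcomes and two-sided 0.05, and the interaction's SE also rests on ρ = 0.5. Drug concentration and the drug-to-substrate ratio are unaffected. The visit 2 data can help to separate the two explanations, but only on the assumption that nothing shifts between visits 2 and 4.

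**What to change.** In the SAP, and in the wording of the Goal:

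1. For immune cell proportions and in vitro infection, name Truvada + gel versus Truvada as the main contrast, using the visit 2 value (for example as a covariate). State the test for the infection assay.
2. Limit the conclusion from that contrast to the lubricant effect in men taking Truvada. Make no abrogation claim from these readouts alone.
3. Report D(lubricant) within its arm, and D(both) − D(lubricant) − D(Truvada), with confidence intervals on a scale fixed in advance, as exploratory only.
4. State beside them that both assume no visit 2 to visit 4 shift, and why one may occur (3 against 10 days' abstinence, earlier biopsy). State that a shift T biases the interaction contrast by −T, and that its SE is about 0.55 SD at 10 per arm if ρ = 0.5.
5. Leave Truvada + gel versus Truvada as the comparison for drug concentration and the drug-to-substrate ratio.

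The cost is SAP and Goal wording and two supportive estimates from samples already planned, with no added men or procedures. What is given up is the stronger claim from the immune and infection data. Supporting that without the no-shift assumption would need a concurrent product-free arm.
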